##### Participants and Recruitment:

Fifty dyads will be recruited from Johns Hopkins primary and affiliated institutions in the greater Baltimore metropolitan area. Index participants engaged in heterosexual relationships will be asked to recruit their main partner for enrollment in the dyadic intervention pilot. The index participant and their partner will contact study staff to be scheduled for a research visit together. Our target is to have complete data on 40 dyads so we set sample size at 50 in order to account for attrition. However, we will stop recruiting when we reach 40 participants.

**Enrollment, Consent, Randomization, and Treatment:** Recruiters will be available via phone during office and some evening hours for the Title X clinical setting. Providers for study contact will refer patients. Patients who agree to be contacted will be approached by a recruiter in person-or via phone and if eligible, the dyad will be scheduled for written informed consent and intervention procedures. At enrollment, the research staff will perform a detailed review of the EXPERIENCE

study with informed consent. While the index patient and their partner are required to present together for study enrollment, they will each be consented separately. Participants will have the option to separately consent for 1) completing both the ACASI and dyadic intervention and 2) additionally completing an in-depth interview. All study protocol study forms will be faxed to the project director at the time of enrollment and online questionnaire/ interview will be automatically uploaded to a secure server for warehousing in a central database. After enrollment, participants will be assigned to the control (1) versus intervention (2) using a computer generated randomization assignment. Envelopes based on dyadic study group number will be available to the research staff at the time of enrollment to adhere to the randomization sequence.

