### **Participants, Recruitment, Enrollment, and Consent for an In-Depth Interview Only:**

Index participants that are screened and eligible for the EXPERIENCE study intervention, but cannot recruit a partner or are not interested in the dyadic intervention will be asked to participate in a one-time in depth interview about AYA sexual health. Consent for the in depth interview only will be a separate form. We expect to enroll up to 40 participants for the in depth interview.

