### **In-depth Interviews**

For a subset of participants, we will conduct separate in-depth, semi-structured, face-to-face and/or via telephone interviews. Participants for the interview will either be 1) enrolled in the EXPERIENCE study intervention and agree to the additional and optional in depth interview or 2) agree to participate in an in depth interview only and not enrolled in the intervention. The interview will explore the social context, specifically social support; relationship qualities, modeling, and communication; and communal coping, that informs AYA partner-dyad's sexual health individually and at the partner level. For those participants that are enrolled in the intervention: the interview will occur 6-8 weeks after the dyad has completed the intervention. For those participants agreeing to an in depth interview only: the interview will be scheduled after written consent is completed. Participants will also be asked to complete a brief demographic questionnaire. We anticipate 40 individual interviews, but will continue sampling until we reach data saturation. The interviews for female and male partners will be conducted separately as to avoid any bias or influence of partner presence in given responses. An in-depth interview guide has been developed for the individual interviews. The semi-structured interview guide focuses on obtaining AYA perceptions of how social context informs sexual health. The concepts of sexual health that will be explored will include sexual experiences, partnering decisions, sexual communication, and prevention of STIs. The development of the interview guide will be an iterative process, which will allow additional questions to be added to the interview guide as necessary. Using the interview guide, the interviewer will ask open-ended questions and seek clarification or elaborations as necessary. All sessions will be audio-recorded and the interviewer will take written notes during and after each interview. During the interview, the interviewee will be asked to refer to themselves, partner(s), and/or other individuals only by an initial to protect confidentiality on recorded audio. Participants who complete the in-depth interview will receive \$50 in remuneration.

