## 5. Inclusion/Exclusion Criteria

**Inclusion Criteria:** The index patient must be 16-25 years, engage in male-female [heterosexual] intercourse, permanently reside in the Greater Baltimore Metropolitan Area (includes surrounding counties, i.e. Baltimore County, Anne Arundel, Howard County), willing to recruit their main sexual partner for the study, are willing to participate in a single individual session with a health educator followed by a joint debriefing session together with both health educators. The partner must be 16-30 years, engage in male-female [heterosexual] intercourse, , permanently reside in the Greater Baltimore Metropolitan Area (includes surrounding counties, i.e. Baltimore County, Anne Arundel, Howard County), willing to recruit their main sexual partner for the study, are willing to participate in a single individual session with a health educator followed by a joint debriefing session together with both health educators.

**Exclusion Criteria:** Index participants and partners who are unable to communicate with staff or participate in study procedures due to cognitive, mental, or language difficulties, will not be eligible for recruitment into the study. Dyads will also be excluded if in same-sex main partnership or a member of the dyad is currently enrolled in another sexual behavior study, the patient/partner is currently pregnant, one or both partners has a known concurrent HIV infection, one or more partners has a pending incarceration, there is more than five years age difference between the two partners, or there is evidence of intimate partner violence [IPV] in the relationship. Couples who are married, engaged or in a committed relationship greater than two years will be excluded. Individuals who screen positive for IPV will be referred to local resources for assistance. The Title X Clinic has adopted the RADAR screening approach with identified social work services in place for registered clinic patients who need further assessment and assistance.

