## 7. Study Statistics

- a. Primary outcome variable. The primary outcome variable for this pilot study is feasibility of recruitment. Recruitment feasibility will be defined as the number of dyads completing the intervention out of number of eligible dyads. The feasibility of short-term retention will be calculated as the proportion of enrolled participants, who complete a follow-up interview at 6 weeks.
- b. Secondary outcome variables. The secondary outcome variable for this pilot study is acceptability, measured as participant satisfaction with their intervention experience. Participant satisfaction will be measured using a brief survey asking participants to rate their experience and qualitative feedback documented.
- c. Statistical plan including sample size justification and interim data analysis.

We will enroll a total of 50 adolescent dyads. While the choice of 50 dyads is inherently arbitrary, it is the number we feel we can realistically enroll within our limited time of this pilot study. While we won't have power to detect statistically significant differences, we will be able to examine correlations, which will be informative for future research proposals. To address each aim, we will evaluate our outcomes, feasibility and acceptability, against benchmarks from previous studies. To address aim 1, we will compare observed recruitment rates from the proposed pilot study to expected recruitment rates. Expected recruitment rates will be determined from previous studies that recruited adolescents with an STI diagnosis. Prior studies recruiting from the Adolescent Medicine Clinic have achieved recruitment rates ranging from 48 to 91%. To address aim 2, we will use a similar approach, comparing satisfaction scores to an a priori benchmark of patient satisfaction. Based on previous work, average patient satisfaction greater than 80% would be necessary to conclude that the intervention is acceptable.

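### Read literally, the primary recruitment rate leaves out eligible index patients who cannot bring a partner, so it cannot reflect failure at the step the design depends on

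*Combined protocol and SAP*

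**What the plan says.** Section 7a names recruitment feasibility as the primary outcome and defines it: "Recruitment feasibility will be defined as the number of dyads completing the intervention out of number of eligible dyads". Section 7c compares observed recruitment with expected rates from earlier studies and cites a range of 48 to 91%.

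Three other places bear on who counts as eligible:

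- **Section 4, Participants and Recruitment.** "Index participants engaged in heterosexual relationships will be asked to recruit their main partner for enrollment in the dyadic intervention pilot". The index patient and partner must present together to enrol. Eligibility is settled at the recruiter's contact with the patient: "if eligible, the dyad will be scheduled for written informed consent and intervention procedures".
- **Section 4, In-Depth Interview Only.** A separate consent route serves index participants who are "screened and eligible for the EXPERIENCE study intervention, but cannot recruit a partner or are not interested in the dyadic intervention". On its size: "We expect to enroll up to 40 participants for the in depth interview".
- **Section 5.** The index patient must be "willing to recruit their main sexual partner for the study" and willing to attend the joint debriefing. The partner has separate criteria. Dyads are excluded on couple-level grounds, including age gap, length of relationship, HIV infection, pregnancy and partner violence.

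The Recruitment Screener (Section 4, Quality Control) records the outcome of each recruitment effort and tracks referred patients who are ineligible or refuse. Nothing in the visible text ties it to the Section 7a denominator.

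**The concern.** The trial enrols couples but begins with one patient, who must then bring the main partner. Objective 1 is to demonstrate feasibility through recruitment and retention, and the partner step is an obvious place for recruitment to fail. The plan foresees that failure, since it provides an interview-only route for these patients.

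A denominator of identified, eligible pairs begins after that step. Two trials with the same pairs and the same completions would report the same primary rate even if one had no unpartnered patients and the other had dozens. Someone planning the next study could take a high rate as evidence that couples can be recruited, when it shows only that couples who came forward went on to complete.

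A second problem concerns the word eligible. The interview-only text counts people with no interest in the dyadic intervention as eligible. Section 5 makes willingness to recruit the partner and attend the joint session a condition of inclusion. Both cannot hold as written, and the answer changes any patient-level denominator.

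**Working it through.** **No figure to reproduce.** The plan gives no expected value for this rate, no partner-recruitment rate and no number to be screened. Section 7c calls the choice of 50 dyads arbitrary, so no power calculation is involved.

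**Notation.** C = dyads completing the intervention; L = eligible pairs that do not complete; U = index patients who meet the index criteria but form no dyad.

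- Rate per eligible pair = C / (C + L)
- Rate per eligible index patient = C / (C + L + U)

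U appears only in the second formula.

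**Inputs, all assumed.** C = 40 and L = 10. These echo the plan's 40 dyads with complete data out of 50 enrolled, but the plan does not predict completion among eligible pairs. U is varied up to 40, the upper figure for the interview-only route. The true U could be lower: the In-depth Interviews section covers both routes and says "We anticipate 40 individual interviews, but will continue sampling until we reach data saturation". It could also be higher, because unpartnered patients who decline the interview would count too.

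| U | Per pair | Per index patient |
|---|---|---|
| 0 | 40/50 = 80% | 40/50 = 80% |
| 10 | 40/50 = 80% | 40/60 = 67% |
| 20 | 40/50 = 80% | 40/70 = 57% |
| 40 | 40/50 = 80% | 40/90 = 44% |

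**Against the 48% floor.** 40/0.48 = 83.3 and 83.3 − 50 = 33.3. So U = 33 gives 40/83 = 48.2%, still in the range, and U = 34 gives 40/84 = 47.6%, below it.

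**Sensitivity.** Crossing the floor depends on the assumptions. At U = 40, C = 40 with L = 0 gives 40/80 = 50%, and C = 50 with L = 10 gives 50/100 = 50%. Both stay inside the range, although the per-pair rates are 100% and 50/60 = 83%.

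**Sampling error.** Exact 95% intervals are 66% to 90% for 40/50 and 34% to 55% for 40/90. At U = 40 the choice of denominator matters more than sampling error, although the second interval still includes 48%. At U = 10 the interval for 40/60 is 53% to 78%, which overlaps the per-pair interval.

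**The group with no interest.** Suppose the 40 split evenly (an assumption) between patients who could not recruit a partner and patients not interested. Counting both gives 40/90 = 44%. Leaving out the second group gives 40/70 = 57%. The unreconciled wording alone moves the rate by 13 points in this example.

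**The case against.** **The failure would be visible anyway.** A reader might infer that no result of this trial could reveal a failed partner step. The documents do not support that. The screener records recruitment outcomes, the interview-only route has its own consent, and a shortfall against the dyad target would show. The limitation is in the primary rate itself.

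**A counting rule may exist elsewhere.** Figure 1, the recruitment algorithm, is not shown and may set out the eligibility steps, so it cannot be said that the plan has no rule. Section 7 does not refer to the figure in the visible text, and the disagreement between Section 5 and the interview-only text does not depend on it.

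**The sponsor may already intend a patient-level count.** Eligibility is judged at the patient's contact, and the interview-only text calls unpartnered patients eligible. If that is the intention, the denominator problem has no numerical effect and one sentence settles it. But the definition says dyads, Section 5 applies exclusions to dyads, and the interview-only text speaks of eligible index participants, so the pair reading is the literal one.

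**The numerator should be enrolment.** This too is tempting, because the outcome is named recruitment but counts completion. Completion is stated explicitly, and consent and intervention are scheduled together. There is no error to correct there.

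**A patient-level denominator could be unfair.** This objection stands in part. Counting every index patient would treat couples excluded by protocol as recruitment failures, so the remedy must remove them.

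**The interview-only wording may be loose.** It could mean patients who met the other criteria and then declined. That is plausible, but the passages still need reconciling.

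**Conclusion.** The concern holds for the visible text. Taken literally, the primary rate starts after the partner-recruitment step and cannot reflect failure there. It can therefore overstate feasibility relative to the 48 to 91% range. In the illustration, 80% per pair corresponds to 67%, 57% or 44% per eligible index patient with 10, 20 or 40 unpartnered patients. All these counts are assumed, and other plausible counts stay inside the range.

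The direction is certain: with fixed C and L, the per-patient rate can never exceed the per-pair rate. The size is unknown.

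A reader might also infer that the benchmark is mismatched in a known direction because it comes from studies that recruited adolescents. The documents do not say how those rates were calculated. The Background describes an earlier cohort, drawn partly from the same clinic, that yielded 132 dyads, and the plan does not say whether it is in the range. The supportable point is that the unit of the benchmark should be stated.

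This should be fixed, because it concerns the primary outcome of a pilot whose stated purpose is feasibility.

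**What to change.** In Section 7a:

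1. Keep completing dyads as the numerator.
2. Set the primary denominator as screened index participants who meet the index-level criteria, including those who cannot bring a partner.
3. Leave out participants whose couple is found ineligible under Section 5, and report them on their own line.
4. Report the per-pair rate beside the primary rate.
5. Report the cascade from the screener: eligible index participant, partner brought, dyad eligible, enrolled, completed.

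Reconcile Section 5 with the interview-only text on people not interested in the dyadic intervention, and show that group separately. In Section 7c, state whether the 48 to 91% rates are per patient or per dyad, and compare like with like.

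**Cost.** These are mainly text changes. The screener already records recruitment outcomes, but it may need a code for failure to bring a partner. The COVID-19 Procedures show that enrolment is under way, so some existing screening records may need recoding. The new rate may be lower than the per-pair rate. Couple eligibility may be unknown where a partner never comes forward; those patients would stay in the denominator, and their number should be stated.

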### **Quality Control**

**1. Treatment Fidelity:** Drs. [name] and [name] [with technical assistance [TA] for specific interventions] will train and supervise research staff to ensure protocol execution with dyads.

**2. Recruitment Screener:** Includes collection of basic demographic data and the outcome of recruitment effort so that we can keep an accurate account of referral patients who are ineligible and/or refuse to participate in the intervention. We include a standard question about (intimate partner violence) IPV in the screener to determine if this is a reason for refusal and/or influence the communication/behavior in the relationship over time. Participants who screen positively, will be provided with information and resources about IPV in the individual visit and referrals placed to the primary health provider for additional services.

**3. Surveys:** We have developed a survey to collect sexual and reproductive health history, perceived barriers to treatment, and self-efficacy data to be administered online during the study visit. This interview will be modified for this study, but will include: demographics, reproductive and sexual history (# partners, partner status (main versus casual), relationship status, coital frequency, prior STIs, condom use consistency, contraceptive use preferences for partner notification (e.g. female partner notification, case worker notification, email, text message), emotional response to diagnosis, access to medical care, access to technology (phone, internet, text), social provisions scale, and the short-form survey instrument (SF-12) as a measure of health-related quality of life, Fertility Knowledge and Awareness Scale, clinical symptoms, sensation seeking scale, relationship qualities scale and intimate disclosure scales to measure relationship quality and dyad communication, childbearing motivation and communal coping. We will also query patients at the end of the intervention to determine their level of confidence for negotiating with their partner and their satisfaction with the experience. It is important to test these measures with participants and the timing of completion.

Participants will be contacted in 6-8 weeks for a brief (~30 min) telephone (or in-person) follow-up interview to assess sexual risk-taking behaviors, relationship status, social support, and satisfaction with the intervention experience.

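### Recruitment feasibility is judged only by completing over eligible dyads, so a shortfall from few eligible couples or slow accrual would not show

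*Combined protocol and SAP*

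**What the plan says.** Section 7a (Study Statistics) states: "The primary outcome variable for this pilot study is feasibility of recruitment". It then gives the measure: "Recruitment feasibility will be defined as the number of dyads completing the intervention out of number of eligible dyads". Six-week retention is a further feasibility measure, also a proportion.

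Section 7c gives the evaluation: "To address aim 1, we will compare observed recruitment rates from the proposed pilot study to expected recruitment rates". The expected rates come from earlier work: "Prior studies recruiting from the Adolescent Medicine Clinic have achieved recruitment rates ranging from 48 to 91" percent. The section does not say which point in that range counts as success. Acceptability, by contrast, has an explicit mark of more than 80% satisfaction.

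On size, Section 7c says "We will enroll a total of 50 adolescent dyads" and gives the reason that "it is the number we feel we can realistically enroll within our limited time of this pilot study". Section 4 (Participants and Recruitment) sets a target of complete data on 40 dyads, explains 50 as an allowance for attrition, and then says recruitment stops at 40 participants. None of these numbers is tied to the feasibility conclusion.

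Section 5 has a long list of exclusions, for example "Couples who are married, engaged or in a committed relationship greater than two years will be excluded". It also makes willingness to recruit the partner and to attend the sessions part of eligibility. The recruitment screener (Section 4, Quality Control) is there so that "we can keep an accurate account of referral patients who are ineligible and/or refuse to participate in the intervention".

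**The concern.** A couple-based pilot can fail to recruit in at least three ways: eligible couples decline or do not complete, too few eligible couples are found, or couples arrive too slowly. A ratio with eligible dyads in the denominator measures only the first. The Section 5 exclusions act before a dyad enters the denominator, so if they remove most couples, numerator and denominator shrink together. Time appears nowhere in the ratio.

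This matters because the plan's stated reason for its size is a claim about accrual within limited time, and the primary outcome does not test that claim. Section 7c expects the results to inform future research proposals. A reader of the primary result alone could take recruitment to be in line with expectation when the supply of couples was the real obstacle.

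**Working it through.** **Inputs from the documents.** Ratio: completing dyads / eligible dyads (7a). Benchmark: 48 to 91% (7c). Planned enrolment: 50 dyads (7c). Target with complete data: 40 dyads (Section 4).

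**The plan's own figure.** No power or precision calculation is given, so there is none to reproduce. The step from 40 to 50 matches 40 / (1 − 0.20) = 50. The 20% attrition is implied by 1 − 40/50, not stated, and Section 7c itself calls the number arbitrary.

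**Step 1: does the ratio respond to scale?** About a quarter of 50 is 12 dyads. Intervals are exact (Clopper-Pearson) 95%.

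| Completing / eligible | Ratio | 95% CI | Against 48–91% |
|---|---|---|---|
| 48 / 72 | 67% | 55–77% | inside |
| 12 / 18 | 67% | 41–87% | inside |
| 12 / 25 | 48% | 28–69% | at lower end |
| 12 / 26 | 46% | 27–67% | below |
| 12 / 50 | 24% | 13–38% | below |

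The first two rows differ four-fold in yield and have the same ratio; only the interval, which the plan does not ask for, differs. The last row shows the opposite case: when the same 12 dyads come from low uptake, the ratio falls well below the range. Likewise 48 of 72 is 67% however long it took.

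**Step 2: when would 12 completing dyads pass?** This needs a pass mark, which the plan does not state. The largest eligible count that still passes is 12 / mark, rounded down.

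- Mark 48%: 12 / 0.48 = 25 eligible dyads.
- Mark 69.5% (middle of the range): 12 / 0.695 = 17.3, so 17.
- Mark 91%: 12 / 0.91 = 13.2, so 13.

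**Step 3: how often would a small pilot pass?** Assume a true ratio of 60%, inside the plan's range, and take the exact binomial probability that the observed ratio reaches the mark.

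| Assumed mark | 20 eligible (12 expected to complete) | 83 eligible (about 50 expected) |
|---|---|---|
| 48% | 0.87 | 0.99 |
| 69.5% | 0.25 | 0.04 |
| 91% | about 0 | about 0 |

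At 48% and a true ratio of 55%, the two figures are 0.75 and 0.91. The chance of passing depends heavily on the mark and the true ratio. At none of these marks does the criterion ask how many dyads were obtained; at 69.5% the smaller pilot passes more often, because its ratio is noisier.

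**Step 4: what is in the denominator?** Because willingness is an eligibility criterion, some reluctant couples may never be counted as eligible. Section 4 also calls index patients eligible when they cannot bring a partner and are offered the interview only, without saying whether each counts as an eligible dyad. If not, failure to bring a partner also drops out of the ratio.

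**The case against.** The strongest reply is that the ratio does depend on recruitment, because completing dyads are its numerator. With 72 eligible dyads, 50 completing gives 69% and 12 gives 17%. Refusal, failure to attend together and non-completion are all detected to the extent that those couples are counted as eligible. This stands. A reader might infer that the conclusion hardly depends on how many dyads are recruited, or that a pilot at a quarter of plan would still be called feasible. The documents support neither: the first is wrong for a given eligible pool, and the second needs both a small pool and a pass mark the plan never sets.

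It can also be said that scarcity of couples is not shown to be likely. Section 4 (Setting) reports over 200 positive cases and partner referrals a year at the clinic, with other referral sites besides. That is fair, and no probability of scarcity is claimed here. But case flow is counted before the Section 5 exclusions, and the criterion does not use it.

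A shortfall would not be concealed either: the screener records ineligible and refusing referrals, the monitoring committee receives annual reports, and enrolment can be set against 50. This also stands, but none of it enters the primary outcome.

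Finally, requiring 50 dyads would clash with Section 4, which stops recruitment at 40, and a time-based pass or fail would need a recruitment period the documents do not give and would be confounded by the COVID-19 change. Both points are right and shape the fix.

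**Conclusion.** The concern holds in a limited form. The primary outcome has no absolute or per-time recruitment target, so a shortfall due to few eligible couples or slow accrual would not show in it, while low uptake among couples counted as eligible would. The contrast is 12 of 18 (67%, the same as 48 of 72) against 12 of 50 (24%).

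That the criterion is a ratio without a count or a time unit is plain from Section 7 and needs no assumption. Any statement about passing does: if 48% is the mark, 12 completing dyads pass only with at most 25 eligible. The probabilities further assume a true ratio of 55 or 60%, and they illustrate the behaviour of the measure rather than forecast the result. The missing pass mark is itself a gap, since without it no ratio leads strictly to a conclusion.

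**What to change.** 1. **Reconcile the target first.** Section 7c plans 50 dyads enrolled; Section 4 aims for 40 dyads with complete data and stops at 40 participants. State one target and one unit. If the stopping rule means 40 individuals, that is 20 couples and the 40-dyad target could not be met.
2. **Add yield to the criterion in Sections 7a and 7c.** For example: recruitment will be concluded feasible only if the ratio meets its benchmark and the target of 40 dyads with complete data is reached. Name the point in 48 to 91% that serves as the benchmark, and say whether eligible index patients without a partner count in the denominator.
3. **Report supply and pace.** From the screener and enrolment dates, give eligible dyads per patient screened and dyads enrolled per month, each with a 95% confidence interval, separately before and after the move to virtual recruitment (Section 4, COVID-19 Procedures). These are descriptive, with no time-based pass mark.

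**Cost.** Mainly protocol wording, plus agreement on the target. The screener already tracks ineligible and refusing referrals, and enrolment dates should exist. The downside is that a pilot that under-accrues can no longer be reported as feasible on the ratio alone.
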